3.1. Rationale for Approach

The total starting dose of 2x10⁹ TCID₅₀ to be used in **Low Dose Cohort E** was chosen based on the following observations:

1. The range of PVSRIPO doses to be administered by intratumoral injection via cystoscopy to patients with MIBC in the bladder cancer substudy is 1x10⁸ to 6x10⁸ TCID₅₀. Since the total dose of 2x10⁹ TCID₅₀ will be diluted into a final volume of 60 mL for intravesical instillation, the bladder mucosa/tumor will be exposed to a PVSRIPO concentration of 3.33x10⁷ TCID₅₀/ml which is ½ to 1 log lower than would be expected with direct intratumoral injection.
2. CVA21, a virus similar to PVSRIPO (both are classified Picornaviridae, Enterovirus) has been administered as repeat dose (Day 1 and Day 2) monotherapy (or in combination

with intravesical mitomycin C) via intravesical instillation (30 ml) to patients with recurrent NMIBC at a total dose of 3×10^8 TCID₅₀ per day. Patients receiving this dose of CVA21 experienced minimal toxicity and limited efficacy (Section 1.1.2) suggesting that evaluating a higher dose to improve efficacy would be safe and tolerable (Annels 2019).

3. Nadofaragene firadenovec is a replication-deficient recombinant adenovirus with a human interferon alfa-2b payload that has been administered at a total dose of 2.25×10^{13} viral particles via intravesical instillation (75 ml) to patients with recurrent NMIBC. Patients who received this dose—which is up to 4 logs higher than the 2×10^9 TCID₅₀ PVSRIPO dose—experienced few (4%) Grade 3 drug related AEs and no Grade ≥ 4 AEs (Boorjian 2020).
4. Each stock vial contains 2×10^9 TCID₅₀ PVSRIPO such that using a starting dose of 2×10^9 TCID₅₀ will facilitate easier handling in the pharmacy and decrease the possibility of errors in preparation and handling.

In summary, a dose of 2×10^9 TCID₅₀ PVSRIPO represents a reasonable starting dose in that it falls within the range of the PVSRIPO dose predicted to be delivered by intratumoral injection and the dose of similar viral products delivered by intravesical instillation where safety and tolerability were acceptable.

An increase in PVSRIPO dose to 1×10^{10} TCID₅₀—which is an increase of 1 log—was chosen to ensure that the higher dose was sufficiently different from the lower dose to facilitate evaluation of any potential dose/response (dose/toxicity) relationship.

The dose of PVSRIPO administered in **Cohort F** will be the highest dose evaluated in **Cohort E** which does not exceed the maximum tolerated dose. Since the bladder washes implemented in **Cohort F** are predicted to improve PVSRIPO infectivity of the bladder mucosa, the highest tolerable PVSRIPO dose administered without washes was chosen to maximize potential patient benefit. As discussed above, preclinical and clinical data suggest that adding washes to the intravesical instillation of viruses does not increase clinically relevant toxicity (Burke 2012).

The timing of PVSRIPO administration prior to TURBT or cystectomy was chosen to be 2 to 5 days based on the following criteria:

1. Delaying TURBT or cystectomy by 2-5 days is not predicted to have a substantial impact on the clinical outcomes of the patients.
2. Preclinical studies with intratumoral injection of PVSRIPO suggest that PVSRIPO replication lasts for approximately 1-2 weeks after injection with peak viral load within 5 days of injection, such that PVSRIPO should still be detectable in the tumor tissue (Yang 2021).
3. Preclinical studies suggest that the innate immune effects of intratumoral injection of PVSRIPO peak before 5 days post treatment such that collecting tissue at 2-5 days will optimize the probability of seeing an effect.

PVSRIPO in combination with anti-PD-1/L1 therapy is not being investigated in this substudy because NMIBC has an exceedingly good prognosis such that systemic therapies with their associated toxicities are generally not used in this patient population because of the poor risk/benefit profile.

4. STUDY POPULATION

Eligibility criteria described in this section are in addition to those described in the master protocol ([Section 4 \[Study Population\] of the Master Protocol](#)) and are specific for **Cohort E and F**: patients with recurrent NMIBC intended for TURBT or cystectomy.

4.1. Inclusion Criteria

Patients are eligible to be included in the study only if all of the following criteria apply:

Both Cohorts:

1. Prior history of stage Ta, T1, or Tis urothelial carcinoma of the bladder.
 - a. Tumors with up to 50% squamous or glandular differentiation are eligible.
 - b. History of variant bladder histologies are excluded (e.g. sarcomatoid, plasmacytoid, small cell or neuroendocrine, pure squamous cell carcinoma, pure adenocarcinoma, micropapillary, nested, lymphepithelioma-like, clear cell)
2. Documented tumor recurrence at cystoscopy where the tumor is amenable to TURBT or cystectomy.
3. Measured or calculated (per institutional standard) creatinine clearance ≥ 45 ml/min (glomerular filtration rate [GFR] can also be used in place of creatinine clearance).
4. If the patient has an available formalin-fixed paraffin-embedded (FFPE) tumor specimen with an associated pathology report documenting NMIBC, the specimen must be confirmed to be available to send to the Sponsor. Patients **without** an available FFPE specimen are still eligible to enroll.
5. Measurable disease per Response Evaluation Criteria in Solid Tumors (RECIST) 1.1 is NOT required. This is an exception to the inclusion criterion outlined in the master protocol.

4.2. Exclusion Criteria

Patients are excluded from the study if any of the following criteria apply:

Both Cohorts:

1. Patients with exposure to intravesical agents (e.g. BCG, mitomycin C, epirubicin, oncolytic viruses, anti-PD-1/L1 inhibitors, investigational therapies, etc.) within 3 months prior to the administration of PVSRIPO.
2. Patients whose anticoagulation or antiplatelet medications cannot be managed by local institutional guidelines to accommodate the safe intravesical instillation of PVSRIPO followed by TURBT, as determined by the treating physician.
3. Received prior radiation to the pelvis.
4. Received prior systemic therapy for bladder cancer, including PD-1/L1 inhibitors.
5. History of vesicoureteric reflux or an indwelling urinary stent.

6. History of stage T2 or higher bladder cancer
7. Medical conditions (as determined by the investigator) that would interfere with the ability of the patient to retain urine for 2 hours. Examples include urinary incontinence, overactive bladder, or low bladder compliance.

5. STUDY TREATMENT

Information regarding discontinuation of study treatment, discontinuation/withdrawal from the study, treatment beyond progression, patients who are lost to follow-up, and site and study termination can be found in [Master Protocol Section 5 \(Study Treatment\)](#).

5.1. Study Drugs Administered

Study drugs are defined as any investigational agent(s) or marketed product(s) intended to be administered to a study patient according to the study protocol. Study drugs used in this protocol are described in [Table 4](#).

Table 4: Study Drugs

Name	PVSRIPO
Type	Investigational Product
Dose Formulation	50 mM sodium phosphate in 0.9% sodium chloride, pH 7.4 with 0.2% human serum albumin (HSA) in phosphate buffered saline (PBS).
Unit Dose Strength(s)	Refer to the Pharmacy Manual
Dosage Level(s)	Described in Section 3
Route of Administration	Intravesical
Use	Experimental
Packaging and Labeling	Study drug will be provided in sterile, single use containers. Each single use container will be labeled as required per country requirement.

5.1.1. Dose, Dosing Regimen, Route, Preparation and Handling

5.1.1.1. PVSRIPO

Cohort E: Each dose of PVSRIPO will be administered in a final volume of 60 ml by intravesical instillation; see the Pharmacy Manual for detailed instruction on how to prepare PVSRIPO for intravesical instillation. A urinary catheter will be inserted into the urethra under aseptic conditions according to local hospital protocol and the bladder drained completely. Using a catheter adapter with the syringe, the PVSRIPO suspension will then be instilled into the bladder via the catheter over a period of several minutes per local practice. After instillation the catheter will be removed, and the patient instructed to retain the instilled suspension in the bladder for a period of 2 hours. During this period, care should be taken to ensure that the instilled suspension has sufficient contact with the whole mucosal surface of the bladder. The patient should be encouraged to mobilize or, if lying down, to rotate between prone, supine, left lateral, and right lateral positions every 15 minutes.

After 2 hours the patient should void the instilled suspension directly into a toilet. After bladder evacuation, the next first voided urine sample should be collected for PVSRIPO Shedding.

The patient should be advised to limit their fluid intake for 4 hours prior to instillation and until bladder evacuation is permitted (i.e. 2 hours after instillation).

Cohort F: Each patient will receive the following sequence of bladder washes prior to instillation of PVSRIPO: 100 ml saline followed by 75 ml 5% DDM followed by 100 ml saline. A urinary catheter will be inserted into the urethra under aseptic conditions according to local hospital protocol and the bladder drained completely. Using a catheter adapter with the syringe, each successive wash will be instilled over a period of several minutes per local practice. Each saline wash will be retained in the bladder for approximately 5 minutes and the 5% DDM wash will be retained within the bladder for 15 (± 5) minutes. At the end of each retention period, the bladder will be drained completely, and the next wash applied. Upon completion of the three washes, PVSRIPO will be instilled as described for **Cohort E** and in the Pharmacy manual. The process for pretreatment washes has been adapted from the process described for CG0070 (Burke 2012).

Both Cohorts:

The dose and dose escalation approach for PVSRIPO is described in [Section 3](#). The timing of administration is outlined in [Table 1](#); in general, PVSRIPO will be administered 2-5 days prior to TURBT or cystectomy.

PVSRIPO preparation, handling, and administration should be performed in accordance with the Pharmacy Manual.

Only staff trained in cystoscopy and intravesical instillation who have read the Pharmacy Manual are allowed to administer PVSRIPO.

Patients should not have a UTI at the time of treatment, as determined by the Investigator. Prophylactic antibiotics should be administered 1-3 days pre-treatment, on the treatment day, and 1-3 days post-treatment to reduce the likelihood of a procedure-related UTI.

Anticoagulant and antiplatelet medications will be managed by the treating physician, per local institutional guidelines, to optimize the safety of intravesical instillation of PVSRIPO.

Investigators should confirm that patients are suitable for the administration procedure prior to each planned administration of PVSRIPO.

5.1.1.2. Intervention After Discontinuation of Study Treatment

Patients in either cohort may receive standard of care treatment after TURBT or cystectomy as determined by the Investigator per institutional guidelines; this includes immediate post-operative chemotherapy.

5.2. Dose Modifications and Toxicity Management Guidelines

Detailed dose modification and toxicity management guidelines can be found in the corresponding section of the master protocol ([Master Protocol Section 5.2 \[Dose Modification and Toxicity Management Guidelines\]](#)).

5.3. Concomitant Medications

Concomitant medications described in this section are in addition to those described in the master protocol and are specific for patients enrolled in **Cohort E and F**.

Patients should not have a UTI at the time of treatment, as determined by the Investigator. Prophylactic antibiotics should be administered 1 to 3 days pre-treatment, on the treatment day, and 1 to 3 days post-treatment to reduce the likelihood of a procedure-related UTI.

Patients may be offered appropriate symptomatic care which could include antihistamines for pruritis, phenazopyridine for dysuria, and/or non-steroidal anti-inflammatory medications for pain. Topical or local anesthetics may be used per local institutional guidelines for management of pain associated with injection.

Warfarin is prohibited. Anticoagulant and antiplatelet medications will be managed by the treating physician, per local institutional guidelines, to optimize the safety of intravesical instillation of PVSRIPO.

6. STUDY ASSESSMENTS

Study assessments described in this section are in addition to those described in the master protocol ([Master Protocol Section 6 \[Study Assessments\]](#)) and are specific for patients enrolled in **Cohort E and F**. Adherence to the study design requirements, including those specified in the Schedule of Assessments ([Table 1](#)), is essential and required for study conduct. Immediate safety concerns should be discussed with the study Medical Monitor upon occurrence or awareness to determine if the patient should continue or discontinue study treatments.

The Investigator or Designee will record minimal data in the eCRF of all patients screened and to confirm eligibility or record reasons for screening failure, as applicable.

Procedures conducted as part of the patient's routine clinical management (eg, hematology, clinical chemistry, cystoscopy) and obtained before signing of the informed consent form (ICF) may be utilized for screening or baseline purposes provided the procedures met the protocol-specified criteria and are performed within the time frame defined in the Schedule of Assessments.

Screening assessments may be repeated if the initial evaluation makes the patient ineligible for enrollment.

6.1. Informed Consent

Patients and the authorized person obtaining the informed consent will be required to sign a statement of informed consent prior to the conduct of any study-related procedures. The Investigator or Designee will explain the nature of the study to the patient and answer all questions regarding the study.

Eligibility should be determined after the patient signs the informed consent and prior to the start of study treatment. Eligible patients will be instructed on all protocol requirements, including any restrictions on concomitant medication usage.

6.2. Safety Assessments

Details regarding AEs, SAEs, and AESIs are provided in [Section 6.1 \(Adverse and Serious Adverse Events\)](#) and [Section 6.2 \(Adverse Events of Special Interest\)](#) of the Master Protocol.

6.2.1. Demographics

Age, gender, race, and ethnicity will be collected during the Screening period.

6.2.2. Medical History and Solid Tumor Disease History

Medical and surgical history, including past and current conditions and procedures, will be collected. Concomitant medications taken within 28 days prior to Cycle 1 Day 1 will be recorded.

Bladder cancer history, including date of diagnosis and prior surgery (including TURBT), will be recorded.

6.2.3. Vital Signs

The following will be collected per the Schedule of Assessments ([Table 1](#)):

- Body temperature, pulse rate, and blood pressure (diastolic and systolic).
- Blood pressure and pulse measurements should be assessed in the sitting position.
- Blood pressure and pulse measurements should be preceded by at least 5 minutes of rest for the patient in a quiet setting without distractions (eg, television, cell phones).
- Height (Screening visit only) and body weight.

6.2.4. Physical Examination

Full physical examination evaluations at screening should include general appearance, skin, neck, eyes, ears, nose, throat, lungs, heart, abdomen, back, lymph nodes, extremities, and neurological examinations. Subsequent physical exams should include body systems as appropriate (eg, brief physical exam).

Information about the physical examination must be present in the source documentation at the study site. Clinically relevant findings observed **prior** to the start of study drug, should be recorded as medical history. Clinically relevant findings observed **after** the start of study drug until 30 days after the last dose of study drug that meet the definition of an AE must be recorded on the AE eCRF.

6.2.5. Clinical Safety Laboratory Assessments

Hematology, clinical chemistry, coagulation (international normalized ratio [INR], prothrombin time [PT], partial thromboplastin time [PTT], activated partial thromboplastin time [aPTT]), and urinalysis will be performed at the site's local certified laboratory per the schedule outlined in the Schedule of Assessments ([Table 1](#)). Additional tests may be performed at any time during the study as determined necessary by the Investigator or required by local regulations. A list of clinical laboratory tests to be performed is provided in [Table 5](#). Clinical chemistry, hematology, coagulation, and urinalysis results should be reviewed before dosing. Laboratory toxicities will be assessed using the National Cancer Institute (NCI) Common Terminology Criteria for Adverse Events (CTCAE), v5.0.

An abnormal laboratory value is not an AE unless it is considered to be clinically significant. Laboratory parameters for which clinically significant values are noted will be re-measured on the appropriate clinical follow-up arranged by the Investigator. Any laboratory value that remains abnormal at the end of the study and that is considered clinically significant should be followed according to accepted medical standards for up to 30 days or until the values return to normal or baseline or are no longer considered clinically significant by the Investigator. If such values do not return to normal/baseline within a period of time judged reasonable by the Investigator, the etiology should be identified, and the Medical Monitor notified.

If laboratory values from non-protocol specified laboratory assessments are performed at the institution's local laboratory as part of the monitoring of an SAE, then the results should be entered into the eCRF as part of safety reporting.

Table 5: Protocol-Specified Safety Laboratory Assessments

Laboratory Assessment	Parameters					
Hematology	Platelet Count	Hemoglobin				
	Complete Blood Count (CBC) with Differential (% and/or absolute values) for neutrophils, monocytes, and lymphocytes					
Clinical Chemistry	Blood Urea Nitrogen (BUN) or Urea	Serum Creatinine	Lactate Dehydrogenase	Albumin		
	Aspartate Aminotransferase (AST)	Alanine Aminotransferase (ALT)	Alkaline Phosphatase (ALP)	Total Bilirubin		
	Potassium	Sodium	Calcium	Chloride		
	Inorganic Phosphorous or Phosphate	Total Protein	Glucose (non-fasting)	Bicarbonate		
Coagulation	International Normalized Ratio (INR)	Prothrombin Time (PT)	Partial Thromboplastin Time (PTT) OR Activated Partial Thromboplastin Time (aPTT)			
Urinalysis	Semiquantitative dipstick: specific gravity, pH, evaluation of glucose, protein, bilirubin, ketones, leukocytes, and hemoglobin					
	Microscopic examination (including red blood cell, white blood cell, and casts) will be performed, if clinically warranted					
Other Tests	Serum or urine human chorionic gonadotropin (hCG) pregnancy test (for persons of childbearing potential only)					

6.2.6. Electrocardiogram

Standard 12-lead electrocardiograms (ECGs) will be performed in triplicate at Screening (Table 1). Additional ECGs may be performed as clinically indicated at any time during the study. All 12-lead ECGs will be obtained after the patient has been resting for at least 10 minutes and shall be recorded at 25 mm/sec. All ECGs for an individual patient shall be recorded with the patient in the same physical position. The 3 ECG recordings shall be taken within an approximate 5-minute period. A cardiologist is not required to review the Screening ECG.

6.2.7. Evaluation of PVSRIPO Shedding

As described in the master protocol and in the IB, PVSRIPO has been subjected to extensive non-clinical and clinical viral shedding studies, all of which suggest the risk of extra-tumoral PVSRIPO dissemination and shedding is extremely low.

Non-human primate studies in Cynomolgus macaques were unable to detect PVSRIPO in saliva, stool, or urine up to 56 days post intracerebral inoculation, with a PVSRIPO dose of 5×10^9 TCID₅₀ (Dobrikova 2012). Likewise, PVSRIPO shedding was undetected in the stool (the main excretory pathway for polio) of patients treated with PVSRIPO for recurrent GBM following administration of intracerebral doses of up to 1×10^{10} TCID₅₀ or in melanoma patients receiving 3 PVSRIPO injections (1×10^8 TCID₅₀ each).

All patients are required to have received a Center for Disease Control (CDC)-recommended immunizing vaccination against polio virus, as well as a polio vaccine booster prior to study entry, which has resulted in extremely high levels of neutralizing anti-poliovirus antibodies in GBM and melanoma patients who have participated in a previous or ongoing PVSRIPO clinical study. Therefore, the Sponsor believes the risk of extra-tumoral PVSRIPO dissemination and shedding is extremely low.

However, because PVSRIPO shedding in patients with NMIBC receiving PVSRIPO by intravesical instillation has not been characterized, samples will be collected to test for the presence of PVSRIPO in urine and stool for all patients as described in the Schedule of Assessments (Table 1). All samples will be collected and evaluated for the presence of PVSRIPO as described in the laboratory manual.

All samples related to the analysis of viral shedding may be collected during clinic visits, where feasible. Otherwise, samples may be collected at home and brought to the next clinic visit, as appropriate. Refer to the laboratory manual for additional details related to sample collection and storage.

6.2.8. Cystoscopic Photography

Pre- and post-PVSRIPO administration photos of the treated bladder/tumor will be collected (as available) and sent to the Sponsor or Designee for storage. If needed, guidelines for collection and storage of the photographic images will be provided in a separate document.

6.3. Biomarker Assessments

If available (Section 4.1), archival tissue from the most recent tissue biopsy/resection should be collected for each patient within 2 months after enrollment. Additional details are outlined in the laboratory manual.

Pre-dose tissue biopsies are optional and should be collected prior to PVSRIPO administration as outlined in Table 1. Additional details are outlined in the laboratory manual. If at the time of the optional biopsy, it is judged that the biopsy is not clinically feasible (ie, poses an unacceptable medical risk to the patient) as judged by the investigator, then the biopsy should not be performed.

TURBT or cystectomy specimens should be processed per standard of care for local pathological evaluation with an expectation that a portion of the specimen will be made available to the

Sponsor; details are provided in the Laboratory Manual. Pathologic review of resected surgical specimens will be performed per institutional standards, and the final pathologic staging will be recorded in the eCRF. Any remaining tissue (after pathologic review) will be evaluated for the presence of PVSRIPO and changes in the immune milieu within the tumor microenvironment. If any tissue biopsies or surgical specimens are collected as standard of care (even if not specified in [Table 1](#)), any remaining tissue (after standard of care analysis) will be made available to the Sponsor provided the patient agrees by signing consent.

Blood samples should be collected at the time points described in [Table 1](#) and processed as described in the Laboratory Manual.

6.4. Data Safety Monitoring Committee

The external independent DSMC is described in the Master Protocol. The text below is specific for patients enrolled in **Cohort E and F**. The schedule of meetings is as follows:

- When dose escalation/de-escalation decisions are required ([Section 3](#)) prior to initiating enrollment in the next cohort. For example, prior to opening the 1×10^{10} TCID₅₀ intravesical instillation dose in **Cohort E** or prior to opening **Cohort F**.
- Additional reviews may occur based on DSMC requests.
- The DSMC will review any Suspected Unexpected Serious Adverse Reaction (SUSAR) that occurs during the study and may recommend enrollment be paused until the event is reviewed.

Note that the timing of DSMC meetings as outlined in [Section 6.3 of the Master Protocol](#) are superseded by the text above. This change is implemented because the structure of the Phase 1 portion of this substudy is slightly different than that described in the Master Protocol, i.e. the timings outlined in the [Section 6.3 of the Master Protocol](#) are not applicable.

Note that the text below from [Section 6.3 of the Master Protocol](#) will still apply to this substudy.

During the study, accrual of patients will be suspended for the following safety events pending evaluation and recommendations by the DSMC:

- Any Grade 5 AE considered to be at least possibly related to study drug(s).
- If two or more of up to 6 DLT-evaluable subjects in **Cohort E** experience DLTs.
- A death within 30 days of study treatment (other than death related to progressive disease).
- Any unexpected Grade 4 AE considered at least possibly related to study drug(s).

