2. OBJECTIVES AND ENDPOINTS

Objectives and endpoints described in **Table 3** are *in addition* to those described in the master protocol (see [Master Protocol Section 2 \[Objectives and Endpoints\]](#)) and include those specific for **Cohort E and F**. Note that two cohorts of patients will be enrolled: **Cohort E** will include patients with recurrent NMIBC intended for TURBT or cystectomy who will receive PVSRIPO via intravesical instillation and **Cohort F** will include patients with recurrent NMIBC intended for TURBT or cystectomy who will receive PVSRIPO via intravesical instillation after a sequence of 5% DDM and saline washes.

Note that the NMIBC sub study will NOT be treating patients with the combination of PVSRIPO and anti-PD-1/L1, i.e., Phase 2 will not be enrolled in the NMIBC substudy.

Table 3: Objectives and Endpoints *

Objectives	Endpoints
Primary Objectives and Endpoints Phase 1	
Cohort E: To evaluate the safety and tolerability of PVSRIPO monotherapy administered by intravesical instillation to patients with recurrent NMIBC intended for TURBT or cystectomy.	Proportion of patients who undergo TURBT or cystectomy as scheduled. This endpoint replaces the master protocol endpoint described as “proportion of patients who received 1, 2 and 3 injections of PVSRIPO”.
Cohort F: To evaluate the safety and tolerability of PVSRIPO monotherapy administered by intravesical instillation after a sequence of 5% DDM and saline washes to patients with recurrent NMIBC intended for TURBT or cystectomy.	Proportion of patients who undergo TURBT or cystectomy as scheduled. This endpoint replaces the master protocol endpoint described as “proportion of patients who received 1, 2 and 3 injections of PVSRIPO”.
Secondary Objectives and Endpoints Phase 1	
Cohorts E and F: To assess the ability of PVSRIPO administered as monotherapy via intravesical instillation (Cohort E) or intravesical instillation after a sequence of 5% DDM and saline washes (Cohort F) to infect bladder cancer cells in patients with recurrent NMIBC intended for TURBT or cystectomy	Proportion of patients with evidence of PVSRIPO infection in resected tissues. This endpoint replaces the master protocol antitumor efficacy endpoints which include ORR, CBR, DOR, PFS and OS.

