However, if 1 out of 3 patients enrolled in the **Low Dose Cohort E** experience a DLT, the cohort will be expanded by enrolling 3 additional patients. If no additional patient experiences a DLT, then the dose will be considered not to have exceeded the MTD and the next cohort of patients (n=3) will receive a total dose of 1×10^{10} TCID₅₀ (**High Dose Cohort E**) via intravesical instillation. In contrast, if a 2nd patient in the **Low Dose Cohort E** experiences a DLT during the initial enrollment of 3 patients--or expanded enrollment to 6 patients--then the maximum dose will have been exceeded, and the dose will be de-escalated to a dose of 2×10^8 TCID₅₀ (**Lowest Dose Cohort E**). The evaluation of either the **High Dose or Lowest Dose Cohort E** will follow the same process as outlined above and in [Figure 1](#).

Figure 1: Dose Confirmation Scheme

* To evaluate this dose, follow the same process

Cohort F: Once enrollment in **Cohort E** has been completed, **Cohort F** will open to evaluate intravesical instillation of PVSRIPO after a sequence of 5% DDM and saline washes in patients (n=3) with recurrent NMIBC using the highest dose evaluated in Cohort E that does not exceed the maximum tolerated dose. The purpose of **Cohort F** is to evaluate if PVSRIPO infection of cells within the bladder mucosa is facilitated by pretreatment with a detergent able to disrupt the GAG layer of the epithelium.

In the event tissue from a TURBT or cystectomy in a given patient is not available after completion of standard of care pathologic review, that patient may be replaced as long as the dose administered to the replacement patient does not exceed the maximum tolerated dose.

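### In the substudy text, the only accrual suspension that counts DLTs (Section 6.4) names Cohort E, so two or more DLTs in Cohort F may trigger no automatic suspension

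*Combined protocol and SAP*

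**What the plan says.** Section 6.4 introduces its DSMC provisions with "The text below is specific for patients enrolled in" Cohorts E and F. It then keeps a list of four accrual-suspension events from Section 6.3 of the master protocol:

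- a fatal (Grade 5) event at least possibly related to study drug;
- a DLT count, worded "If two or more of up to 6 DLT-evaluable subjects in" Cohort E;
- a death within 30 days of treatment not due to progression;
- an unexpected Grade 4 event at least possibly related to study drug.

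Only the DLT count names a cohort. Scheduled DSMC meetings fall at dose decisions and before the next cohort opens, including before Cohort F. Beyond these, "Additional reviews may occur based on DSMC requests". The DSMC also reviews every SUSAR and may recommend a pause.

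Section 3 writes the 3+3 rule for Low Dose Cohort E and extends it to the High and Lowest Dose levels of Cohort E. Cohort F is a fixed group of 3 with no DLT rule of its own. If a patient's resected tissue is not available, "that patient may be replaced as long as the dose administered to the replacement patient does not exceed the maximum tolerated dose".

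Table 3 gives the Cohort F primary objective as "To evaluate the safety and tolerability of PVSRIPO monotherapy administered by intravesical instillation after a sequence of 5% DDM and saline washes". Table 1 schedules a DLT period for both cohorts. Section 3.1 says the washes "are predicted to improve PVSRIPO infectivity of the bladder mucosa", and that "the highest tolerable PVSRIPO dose administered without washes was chosen to maximize potential patient benefit".

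**The concern.** DLTs are scheduled to be assessed in Cohort F, and safety after the wash is its primary objective, yet no stated count rule in this text acts on them. In Cohort E, two DLTs among the first three patients put the dose above the MTD and suspend accrual. In Cohort F the same result has no stated automatic consequence.

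The wash is the new element. Cohort F patients receive the highest dose cleared without it, and the plan expects the wash to raise infectivity. The DSMC meeting scheduled before Cohort F opens can see only data without the wash.

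Two decisions are left without a rule: whether the remaining planned patient is dosed after two DLTs, and whether a replacement is dosed. Replacement is a real possibility, because the infection endpoint depends on leftover material: "Any remaining tissue (after pathologic review) will be evaluated for the presence of PVSRIPO".

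**Working it through.** **The plan's own figure.** Section 7.1 gives 6 to 12 patients for Cohort E. Two dose levels of 3 to 6 patients give 2 × 3 = 6 and 2 × 6 = 12, so the figure is reproduced. For Cohort F the plan gives n = 3 and no operating characteristics.

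**Which triggers apply.** Take two Cohort F DLTs that are Grade 3, or Grade 4 but expected, and not fatal. That such events count as DLTs is an assumption, because the definition is in the master protocol.

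| Section 6.4 trigger | Met? |
|---|---|
| Related Grade 5 event | No, non-fatal |
| DLT count | No, Cohort E only |
| Death within 30 days | No, non-fatal |
| Unexpected related Grade 4 event | No, Grade 3 or expected |

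None of the four is met. If an event were a SUSAR, DSMC review would follow, but a pause would be a recommendation the committee may make. Section 6 also asks for immediate safety concerns to go to the Medical Monitor, but that concerns whether the individual patient continues.

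**How often it could matter.** Let p be the true DLT rate in Cohort F. The documents give no value; 0.1 to 0.3 is assumed.

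- Two or more DLTs in 3 patients: 3p²(1 − p) + p³.
- First two patients both have a DLT, so that a stop could spare patient 3: p².
- Second DLT falls in patient 3, so that a stop affects only replacements: 2p²(1 − p).

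| p | Two or more of 3 | First two both | Second in patient 3 |
|---|---|---|---|
| 0.1 | 0.027 + 0.001 = 0.028 | 0.01 | 0.018 |
| 0.2 | 0.096 + 0.008 = 0.104 | 0.04 | 0.064 |
| 0.3 | 0.189 + 0.027 = 0.216 | 0.09 | 0.126 |

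The last two columns add up to the second. The p² column is an upper limit: it needs both outcomes to be known before patient 3 is dosed. The DLT window is 14 days, and the substudy text states no interval between Cohort F patients.

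**Replacements.** Let u be the chance that a patient yields no usable tissue. Section 1.1.2 reports a coxsackievirus A21 study with 15 patients and 14 specimens available, without the reason for the gap. This suggests u = 1/15 as one illustration; u = 0.2 is assumed as another. The chance that at least one of 3 patients lacks tissue is 1 − (1 − u)³:

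- u = 1/15: 1 − (14/15)³ = 0.187.
- u = 0.2: 1 − 0.8³ = 0.488.

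Multiplying by the chance of two or more DLTs, with independence assumed, gives for p = 0.1, 0.2 and 0.3:

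- u = 1/15: 0.005, 0.019, 0.040.
- u = 0.2: 0.014, 0.051, 0.105.

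**The case against.** The strongest objection is that the substudy is a supplement. DLT definitions, toxicity management, discontinuation and study termination are all assigned to the master protocol, which was not available. A reader might infer that the trial as a whole has no DLT stop for Cohort F. The documents do not support that; they show only that this text states none. Section 6.4 does present its list as the retained master protocol wording, with Cohort E named, so a site reading it would find no Cohort F count.

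A reader might also infer that replacements are permitted after two Cohort F DLTs. That goes too far as well. Replacement is conditional on the MTD, and a DSMC could reasonably decide that two DLTs in three washed patients fail that condition. The only MTD rule in the text is Cohort E's, so the wording is ambiguous, not permissive.

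The plan also gives grounds to expect little added toxicity. Section 3.1 cites data suggesting that washes do not add clinically relevant toxicity, and Section 1.2 predicts low to negligible extra irritation. Section 1.1.2 reports 35 patients given CG0070, the product from which the wash procedure was adapted: the most common events were transient Grade 1 or 2, with no related serious events. This stands, and it is why DLT rates of 0.4 or 0.5 are not used here. It is not conclusive, because the animal irritation data used 0.1% DDM, one-fiftieth of the 5% planned, and the clinical experience is with a different virus.

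Finally, Cohort F leads to no further dose level, so the Cohort E comparison is imperfect. That is true, but safety after the wash is still its primary objective.

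**Conclusion.** The point holds for the substudy text. Section 6.4 claims to cover both cohorts, but its only DLT-count suspension covers one, and the replacement condition is silent on Cohort F DLTs. Two or more such DLTs outside the other three triggers lead only to review routes in which a pause is discretionary.

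The size is small. At assumed DLT rates of 0.1 to 0.3, two or more DLTs occur in 3% to 22% of trials, and a rule would spare planned patient 3 in at most 1% to 9%. In the rest of those trials it would govern only replacements. The conclusion assumes that Grade 3 or expected Grade 4 events can be DLTs and that no master protocol rule already covers Cohort F. The correction is worth making because it changes a stated safety rule at very little cost.

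**What to change.** 1. In Section 6.4, reword the trigger to cover two or more DLT-evaluable subjects in any Cohort E dose level (up to 6) or in Cohort F. If a master protocol rule already covers Cohort F, cite it there instead.
2. In Section 3, state that after two Cohort F DLTs no further Cohort F patient, including a replacement, is dosed pending DSMC review.

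No extra patients or assessments are needed, since Table 1 already schedules the DLT period for both cohorts. The cost is a text amendment, one possible extra DSMC review, and possibly one fewer tissue sample from patient 3 or a replacement. With three patients, losing patient 3's sample would remove a third of the Cohort F infection data. The section 6.4 wording should be checked against the master protocol before it is changed.
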